2.8.6. Partial Subsequent Anticancer Therapy Start Date

If year or month of subsequent anticancer therapy start date is missing or no components of the start date are present, no imputation will be performed.

If only the day-component is missing, the following steps apply:

- If the month and year of the start date are the same as the month and year of last dosing date, the day of last dosing date or the day-component of the stop date of subsequent anticancer therapy is imputed, whichever is earlier.
- If the start month and year are not the same as the month and year of last dosing date, the first day of the month is imputed.

If after the above imputation are applied, the imputed start date is after the non-imputed end date then re-adjust the start to be the same as the end date.

No imputation will be applied for missing or partial subsequent anticancer therapy end date.

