4.3.1. Progression-free Survival (PFS)

Definition

PFS is defined as the duration from the date of the first daratumumab dose to the date of progression/relapse or death (prior to subsequent systemic anticancer therapy or withdrawal of consent to study participation or lost to follow-up) due to any cause, whichever comes first.

If a subject started subsequent therapy or withdrew consent to study participation or lost to follow-up, PFS will be censored at last disease assessment prior to the date of the start of subsequent therapy or date of withdrawal of consent or lost to follow-up. Subjects who have not progressed and are still alive at the cut-off date for analysis will be censored at the date of last disease assessment. Subjects without any post-baseline disease assessment will be censored at the date of first Dara dosing.

Analysis Methods

Analysis of PFS will be based on all treated population. The Kaplan-Meier method will be used to estimate the distribution of overall PFS for each NHL subtype. The median PFS will be provided. In addition, the number and percentage of subjects who had progression disease or were censored will be reported. The Kaplan-Meier PFS curve will also be plotted by NHL subtype.

Additionally, reasons for PFS and censoring will be summarized for all treated subjects.

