5.1. Adverse Events

All adverse events whether serious or non-serious, will be reported from the time a signed and dated ICF is obtained until 30 days after the last dose of study treatment, until the subject withdraws consent for study participation, or until the subject starts subsequent anticancer therapy, whichever occurs first. AEs will be recorded in standard medical terminology and graded according to the National Cancer Institute Common Terminology Criteria for Adverse Events (NCI-CTCAE), Version 4.03. For AE reporting, the verbatim term used in the CRF by investigators to identify adverse events will be coded using the latest version of Medical Dictionary for Regulatory Activities (MedDRA) coding dictionary.

Unless otherwise specified, at each level (e.g., system organ class and/or preferred term) of subject summarization in reporting the incidence of the AE, a subject is counted once if one or more events were recorded.

All summaries of AEs will be based on treatment-emergent adverse events (TEAEs). TEAEs are defined as any AE that occurs after start of the first study treatment through 30 days after the last study treatment; or the day prior to start of subsequent anticancer therapy, whichever is earlier; or any AE that is considered drug-related (very likely, probably, or possibly related) regardless of the start date of the event.

The incidence of TEAEs will be summarized overall, by MedDRA system organ class (SOC) and preferred term, by toxicity grade, and by relationship to study treatment administration. Specifically, the following AE summaries will be presented by NHL subtype:

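### SAP 2.8.6 can date a subsequent therapy with a missing start day before a documented same-month progression, which turns that PFS event into a censoring; it can also date it on or before the last infusion.

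*SAP*

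**What the plan says.** SAP 2.8.6 has two branches for a start date that lacks only its day.

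- Same month and year as the last daratumumab dose: "the day of last dosing date or the day-component of the stop date of subsequent anticancer therapy is imputed, whichever is earlier".
- Otherwise the 1st is used: "start month and year are not the same as the month and year of last dosing date, the first day of the month".

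One adjustment follows, and it can only move the date earlier: if "the imputed start date is after the non-imputed end date then re-adjust the start to be the same as the end date". The date of progression is not used anywhere in the rule.

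SAP 4.3.1 defines the PFS event as "progression/relapse or death (prior to subsequent systemic anticancer therapy or withdrawal of consent to study participation or lost to follow-up"). For a subject who started another therapy, "PFS will be censored at last disease assessment prior to the date of the start of subsequent therapy". With no earlier post-baseline scan the fallback is: "Subjects without any post-baseline disease assessment will be censored at the date of first Dara dosing".

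The same start date feeds two safety derivations. The treatment-emergent window in SAP 5.1 runs to 30 days after the last study treatment "or the day prior to start of subsequent anticancer therapy, whichever is earlier". In SAP 2.1, if the End-of-Treatment visit date is missing, the last cycle ends at the earlier of 30 days after the last dose and the day before subsequent therapy.

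**The concern.** Protocol 9.1.3 makes diagnosed progression a reason to stop treatment. Protocol 9.1.4 lets the regular scans of subjects who stopped early end once a new anticancer therapy starts. The usual order is therefore last dose, PD, new therapy. A rule that picks the last-dose day or the 1st of the month reverses the last two steps whenever PD and new therapy share a calendar month.

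The error runs one way: a documented progression becomes a censoring at an earlier scan. Scans are 8, 16 and then 24 weeks apart (SAP 1.1), so the shift can be long. PFS is a major secondary endpoint, and SAP 1 says this interim plan becomes the study SAP if futility is met. A Stage 1 cohort has 20 or 15 subjects, so one lost event is 1/20 = 5% or 1/15 = 6.7% of it. The planned counts of events and reasons for censoring would be wrong as well.

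**Working it through.** The plan states no figure for this rule, so there is none to reproduce. The check applies the rules as written.

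**Worked cases (dates assumed).** First dose is 15 January 2016. PD is at the week-8 scan, 11 March. New therapy truly starts on 21 March but is recorded only as March 2016. True PFS, with the plus-one-day convention of SAP 2.1, is 56 + 1 = 57 days with an event.

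- (a) Last dose 4 March: the months match, so the imputed start is 4 March, before the PD.
- (b) Last dose 26 February: the months differ, so the imputed start is 1 March, before the PD.

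In both cases the only post-baseline scan falls after the imputed start. The subject is censored at first dose: an event at day 57 becomes a censoring at day 1. Under the PFS definition in Protocol 9.2.2.2, which has no cut-off at new therapy, the event would count.

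**Share of PDs lost among missing-day records.** Inputs are a PD spread evenly over the calendar, a last dose before the PD, no stop date, and a gap of g days from PD to new therapy (assumed). Both branches give a date on or before a same-month PD, so a PD is lost when it shares the therapy's month. That share is about 1 - g/30.4 for g below a month. If a PD on the imputed day itself is kept, subtract about 1/30.4 = 0.03. A day-by-day calendar count gives:

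| Gap (days) | PD on imputed day kept | PD on imputed day lost |
|---|---|---|
| 3 | 87% | 90% |
| 7 | 74% | 77% |
| 14 | 51% | 54% |
| 21 | 28% | 31% |
| 30 | 0% | 2% |
| 45 | 0% | 0% |

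The results are the same for last-dose-to-PD intervals of 7, 14 and 28 days.

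**Averages over a spread of gaps (PD on imputed day lost).** For whole-day gaps from 3 to 28, the mean gap is 15.5 and 1 - 15.5/30.4 = 49%. For wider spreads only gaps of 3 to 30 days contribute: 28 - 462/30.4 = 12.8. Dividing by the number of gap values gives 12.8/40 = 32% for 3-42 days, 12.8/58 = 22% for 3-60 and 12.8/88 = 15% for 3-90.

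**Events per cohort.** Suppose, as an upper bound, that every subject progresses and switches, and assume 10-30% of starts lack the day. For 20 subjects the loss runs from 20 x 0.10 x 0.15 = 0.3 to 20 x 0.30 x 0.49 = 2.9. For 15 subjects it runs from 15 x 0.10 x 0.15 = 0.2 to 15 x 0.30 x 0.49 = 2.2.

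**Safety windows.** In case (a) the imputed start equals the last-dose day, 4 March. The treatment-emergent window closes on 3 March, so an AE after the final infusion that is not judged related drops out. If the End-of-Treatment visit date is missing, the last cycle also ends on 3 March, before its own last dose. A stop date can make this worse, because only its day of the month is compared: last dose 20 March with therapy stopped 5 June gives an imputed start of 5 March.

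**The case against.** Several limits are fair and stand.

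- The effect needs three things together: only the day missing, PD in the month of the new therapy, and PD on or after the imputed day. A PD dated before the imputed last-dose day is kept.
- The 49% average holds only if every subject switches within 28 days of PD. Nothing in the documents supports that spread or any particular missing-day rate, and Protocol 17.6 provides for eCRF review for completeness.
- PFS is a descriptive Kaplan-Meier summary without a test. The summary of censoring reasons (SAP 4.3.1) and the subject listing of progressions (SAP 4.3.4) would help to expose affected cases.
- AEs judged related stay treatment-emergent whatever their date, and the last-cycle effect needs a missing visit date.

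Earliest-date imputation can also be defended as not crediting daratumumab with time on another drug. That does not justify placing the new therapy before a known PD, or on or before the last infusion.

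The parenthesis in SAP 4.3.1 might be read as limiting deaths only. The result is the same, because the next paragraph censors anyone who started subsequent therapy.

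Two stronger readings are tempting. A reader might infer that the rule mainly removes fast progressors. The calculation depends on how soon therapy follows PD, not on how early PD occurs, so this is not shown. A reader might also infer that the Stage 1 decision is affected. It rests on ORR, which has no subsequent-therapy cut-off in SAP 4.2, and DoR in SAP 4.3.4 has none either.

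**Conclusion.** The defect is real and follows from the SAP's own text: applied exactly, 2.8.6 and 4.3.1 can turn a documented progression into a censoring, and no other passage supplied overrides this. From the lost PD onward the Kaplan-Meier curve sits too high. Per missing-day record the share lost ranges from about three quarters at a 7-day gap to about none from a month; averaged over gaps it is about 49% for 3-28 days and about 15% for 3-90 days. These figures rest on assumed gaps and evenly spread PD dates. The number of events lost in this trial cannot be computed from the documents and is probably small per cohort. ORR and futility are untouched. It should be corrected because the rule gives a wrong result and is cheap to change, not because a large bias has been shown.

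**What to change.** In SAP 2.8.6, when only the day is missing, impute the latest of:

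- the first day of the recorded month;
- the day after the last dose, if the last dose is in that month;
- the day after a documented PD, if the PD is in that month.

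Cap the result at the last day of the recorded month and at any complete therapy stop date or death date. Without the month-end cap, a PD on 31 March with therapy recorded as March would give 1 April. Use this date for PFS, the treatment-emergent window and the end of the last cycle.

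In SAP 4.3.1, state that a PD dated on or before an imputed therapy start counts as an event. In cases (a) and (b) the imputed start becomes 12 March and the event at day 57 is kept.

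One edge remains: a last dose on the final day of the month is capped back to the dose day. Not letting the windows in 5.1 and 2.1 end before the last dose would close it.

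The cost is one SAP paragraph, one sentence and a few lines of derivation code, with no new data. The downside is that if therapy truly began before a same-month PD, that PD is counted as an event. List these subjects so the reader can see how many there are.

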2.9. General Analysis Method

In general, continuous variables will be summarized using descriptive statistics such as mean, standard deviation (SD), median and range. Categorical variables will be summarized using frequency and percentage. For time-to-event variables, the Kaplan-Meier method will be used for descriptive summaries.

3. SUBJECT INFORMATION

3.1. Demographics and Baseline Characteristics

Unless specified otherwise, all demographic and baseline characteristics variables will be summarized for the all treated analysis set. No statistical comparisons between the 3 NHL subtypes are planned.

The distribution of subject enrollment will be presented for each cohort according to region and country. Subjects who did not meet study inclusion/exclusion criteria will be listed by subject ID, NHL subtype, and specific criteria not met.

Subject demographic and baseline characteristic variables: age (< 65 years and ≥ 65 years), sex, ethnicity, race, weight (kg), height (cm), and ECOG performance status will be summarized by NHL subtype and overall. A listing of subject demographic and baseline characteristics will be provided as well.

Baseline disease diagnosis including % CD38 and CD59 expression level, CD38 H-score, ratio of CD38 and CD59 expression level, $\beta 2$ -microglobulin, bone marrow % lymphoma cell infiltration, CD5, CD10, CD19, CD20 and months since initial diagnosis will be summarized by NHL subtype and overall. Subtype of Follicular lymphoma (Grade 1, 2, 3A) will be summarized for FL cohort, and subtype of DLBCL molecular (Non-GCB, GCB, Unknown) will be summarized for DLBCL cohort. A listing of disease diagnosis will be provided as well.

Medical history collected at baseline or screening visit will be summarized by system-organ class and preferred term for each NHL subtype and overall.

3.2. Disposition Information

An overview of subject disposition by NHL subtype will be provided. The overview includes a summary of total number of subjects who are treated in each NHL subtype. For all treated subjects, the number and percentage of subjects who discontinued study treatment including reason for discontinuation as indicated by the investigators will be summarized. The similar summaries will be presented for all treated subjects who discontinued from study participation.

In addition, a summary of all screened subjects per analysis set will be reported and a listing of subjects who discontinued study treatment or study participation including reasons for discontinuation will be provided.

3.3. Extent of Exposure

Extent of exposure to study treatment will be summarized and presented based on all treated population.

The number and percentage of subjects treated within each cycle will be summarized by NHL subtype and overall. The maximum number of treatment cycles received for each subject will be summarized by frequency and descriptive statistics.

Duration of study treatment, defined as the number of days from the date of the first administration of study treatment to the date of the last administration of study treatment, will be summarized. The number of daratumumab infusions will be summarized for all treated subjects by NHL subtype and overall.

Daratumumab dose intensity, which is defined as the sum of total dose administered (mg/kg) in all cycles divided by the number of treatment cycles, will be summarized. Additionally, the daratumumab dose intensity will be summarized for cycles with high-intensity (Cycles 1-2) or low-intensity (Cycles 3-6 and Cycles 7+).

The relative dose intensity (%) defined as the ratio of total actually received dose and total planned dose will be calculated and summarized by NHL subtype using descriptive statistics.

The number of subjects with cycle delays or dose modifications (dose delays or dose skipping) including reasons (AE or other) for cycle delays or dose modifications, will be reported.

A listing of subjects with daratumumab infusions will be provided.

3.4. Protocol Deviations

A listing of subjects with major protocol deviations including NHL subtype, subject ID, type of deviation, and reasons for deviation will be provided.

3.5. Prior and Concomitant Medications

A summary of prior therapies (systemic therapy, radiotherapy, or cancer-related surgery/procedure) will be provided by NHL subtype. Specifically, the number of prior lines of therapy will be calculated and summarized by the following categories: 1, 2, or ≥ 3 through frequency and descriptive statistics. Additionally, the prior systemic therapy will be summarized by therapeutic class, pharmacologic class and drug name for each NHL subtype.

For FL cohort, the number of subjects who had prior anti-CD20 medication (rituximab or obinutuzumab) will be provided.

For MCL cohort, the number of subjects who had prior ibrutinib will be provided. A descriptive summary of total number of cycles received for prior ibrutinib will be provided. The incidence of

subjects who received prior ibrutinib in their last line of therapy will be reported. Best response to prior ibrutinib and number of subjects who had progression/relapse from prior ibrutinib will also be summarized.

Concomitant medications collected in the CRF page during the study will be summarized by therapeutic class, pharmacologic class, and drug name for each NHL subtype. A similar summary will be provided for pre-infusion medication and post-infusion medication, respectively. A listing will be provided for pre-infusion medication and post-infusion medication, respectively.

3.6. Subsequent Anticancer Therapy

The total number of subjects who received subsequent anticancer therapy will be reported for each NHL subtype. A summary of subsequent anticancer therapy will be presented by therapeutic class, pharmacologic class and drug name. Specifically, the number of lines of subsequent anticancer therapy will be calculated and summarized by the following categories: 1, 2, or ≥ 3 through frequency and descriptive statistics.

4. EFFICACY

Response and disease progression were assessed by investigators, based on Revised Criteria for Response Assessment (Cheson 2014)¹. The detailed documentation can be found in Attachment 1 in Protocol. Efficacy analyses will be based on all treated population and presented by each NHL subtype.

4.1. Analysis Specifications

4.1.1. Level of Significance

All 95% confidence interval presented will be 2-sided.

4.1.2. Data Handling Rules

There is no imputation planned for missing efficacy endpoint values.

4.2. Primary Efficacy Endpoint(s)

4.2.1. Definition

The major efficacy endpoint, ORR, is defined as the proportion of subjects who achieve CR or PR.

4.2.2. Analysis Methods

For each NHL subtype, an estimate of the ORR will be presented along with a two-sided 95% exact confidence interval. The number and percentage of subjects in the following response categories will be presented by NHL subtype: complete response (CR), partial response (PR), stable disease (SD), progressive disease (PD), not evaluable (NE), overall response (CR+PR) and Clinical benefit rate (CR+PR+SD).

4.3. Major Secondary Endpoints

The major secondary endpoints include PFS, OS, DoR and time to response.

4.3.1. Progression-free Survival (PFS)

Definition

PFS is defined as the duration from the date of the first daratumumab dose to the date of progression/relapse or death (prior to subsequent systemic anticancer therapy or withdrawal of consent to study participation or lost to follow-up) due to any cause, whichever comes first.

If a subject started subsequent therapy or withdrew consent to study participation or lost to follow-up, PFS will be censored at last disease assessment prior to the date of the start of subsequent therapy or date of withdrawal of consent or lost to follow-up. Subjects who have not progressed and are still alive at the cut-off date for analysis will be censored at the date of last disease assessment. Subjects without any post-baseline disease assessment will be censored at the date of first Dara dosing.

Analysis Methods

Analysis of PFS will be based on all treated population. The Kaplan-Meier method will be used to estimate the distribution of overall PFS for each NHL subtype. The median PFS will be provided. In addition, the number and percentage of subjects who had progression disease or were censored will be reported. The Kaplan-Meier PFS curve will also be plotted by NHL subtype.

Additionally, reasons for PFS and censoring will be summarized for all treated subjects.

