#### **9.2.2.2. Major Secondary Endpoints**

Duration of response (DoR) will be duration from the date of the initial documentation of a response to the date of first documented evidence of PD (or relapse for subjects who experience CR). For those subjects who are still without progression/relapse, DoR will be censored at the last adequate tumor assessment.

PFS is defined as the duration from the date of the first daratumumab dose to the date of progression/relapse or death, whichever comes first. For those subjects who are still alive without progression/relapse, PFS will be censored at the last adequate tumor assessment.

Overall survival (OS) is defined as the duration from the date of the first daratumumab dose to the date of death. For those subjects who are still alive without progression/relapse, OS will be censored at the last date known to be alive.

Time to response is defined as the duration from the date of the first dose of daratumumab to the earliest date that a response (CR/PR) is first documented. For non-responders, it will be censored at the date of progressive disease/relapse or the date of the last adequate disease assessment, whichever comes first.

additional sampling is required. Procedures for sample collection, preparation, identification, storage, and shipment will be provided in the Laboratory Manual or equivalent document.

Additionally, blood samples should also be collected at the final visit from subjects who are discontinued from treatment. Subjects who discontinue treatment will also be asked to return for immunogenicity evaluation during the Follow-up Phase.

A blood sample should be drawn, if possible, for determination of antibodies to daratumumab any time an infusion reaction is observed or reported during the study. Daratumumab serum concentration will also be determined from the same infusion reaction sample for the purpose of interpreting immunogenicity data. These samples will be stored and evaluated if deemed necessary. If the infusion reaction results in treatment discontinuation, then subjects should undergo all scheduled safety and efficacy evaluations. Samples collected for the analysis of daratumumab immunogenicity/serum concentration may additionally be used to evaluate safety or efficacy aspects that address concerns arising during or after the study period or for the evaluation of relevant biomarkers by the sponsor or sponsor's designee.

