Alternatively, if the futility criteria are not met and if supported by the totality of the Stage 1 data, Stage 2 for that NHL subtype may be opened for accrual. If the required number of responses is observed prior to completion of enrollment in Stage 1, Stage 2 may be opened immediately upon completion of enrollment to Stage 1, if supported by the totality of data.

Stage 2, if opened, is designed to further evaluate safety and efficacy as well as to determine a threshold for CD38 expression that is associated with enhanced daratumumab activity. Supported by the preliminary activity observed in Stage 1, Stage 2 will enroll any subject in each NHL subtype. To mitigate the possibility that a low response may be observed due to low levels of

CD38 expression in enrolled subjects, the number of Stage 2 subjects with CD38 expression level <50% will be capped within each NHL subtype.

The target number of subjects in each stage by CD38 expression level is shown in table below.

Type of NHL	Number of Subjects			Overall Total
	Stage 1 CD38 expression level ^b ≥50%	Stage 2 (optional)		
		CD38 expression level ^a <50%	CD38 expression level ^b ≥50%	
MCL	20	≤30	≥50	100
DLBCL	15	≤20	≥20	55
FL	15	≤20	≥20	55

DLBCL=diffuse large B cell lymphoma ; FL=follicular lymphoma; MCL= mantle cell lymphoma

a. These subjects have tumors where <50% of the cells are positive for CD38 by immunohistochemistry.

[figure not shown]
b. These subjects have tumors where ≥50% of the cells are positive for CD38 by immunohistochemistry.

Subject participation will include a Screening Phase, a Treatment Phase, and a Follow-up Phase.

The Screening Phase will be up to 28 days prior to Cycle 1, Day 1. Prior to enrollment, subjects are required to provide tumor tissue to determine CD38 expression level by immunohistochemistry (IHC) at a central laboratory. An additional fresh biopsy should be obtained whenever possible even if an archival sample is provided.

The Treatment Phase will extend from Cycle 1, Day 1 until study drug discontinuation. After first dose, disease evaluations will occur every 8 weeks for the first 3 evaluations, then every 16 weeks for the next two evaluations and then every 24 weeks thereafter. Subjects will be treated until disease progression, unacceptable toxicity, or other reasons as listed in the protocol.

A schematic overview of the dosing schedule is presented as follows.

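### SAP 4.3.1 drops the protocol's requirement that the assessment setting a PFS censoring date be adequate, so a not-evaluable scan may set it; the PFS curve can only rise or stay the same

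*SAP*

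**What the plan says.** Protocol section 9.2.2.2 gives one rule for subjects alive without progression or relapse: "PFS will be censored at the last adequate tumor assessment". The same section also uses *adequate* for duration of response and time to response.

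SAP section 4.3.1 has three relevant sentences, none with that qualifier:

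- Alive and progression-free at cut-off: subjects who "have not progressed and are still alive at the cut-off date for analysis will be censored at the date of last disease assessment".
- New anticancer therapy, consent withdrawal or loss of contact: "PFS will be censored at last disease assessment prior to the date of the start of subsequent therapy", and likewise for the other two reasons.
- Fallback: "Subjects without any post-baseline disease assessment will be censored at the date of first Dara dosing".

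SAP section 4.2.2 lists a response category "not evaluable (NE)". On estimation, SAP section 4.3.1 says: "The Kaplan-Meier method will be used to estimate the distribution of overall PFS for each NHL subtype". It adds a median, a plot and a summary of censoring reasons, but no test.

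**The concern.** An NE scan does not establish whether the disease has progressed. If it sets the censoring date, the subject stays in the risk set as event-free through a period in which progression was not ruled out. A subject whose only post-baseline scans are NE would be censored at the last of them instead of at first dose.

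A programmer following the SAP literally and one following the protocol would then derive different PFS times for such a subject. The difference goes one way, towards longer PFS, in an uncontrolled, open-label study with investigator-assessed progression. PFS is a major secondary endpoint. SAP section 1 says this interim SAP becomes the study SAP if the futility criteria are met, so the wording may be final for some or all subtypes.

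**Working it through.** **No plan figure to reproduce.** The documents state no median, event count or power for PFS. The check compares two censoring rules on the same data: (a) last adequate scan, taking adequate to mean not NE, as in the protocol; (b) last scan of any kind, the literal SAP rule.

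**Who is affected.** An NE scan followed by documented progression is still an event at progression. An NE scan followed by an evaluable scan has no effect on the censoring date. Dates differ only for event-free subjects whose last scan before censoring is NE.

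**How far the date moves.** SAP section 1.1 says "disease evaluations will occur every 8 weeks for the first 3 evaluations, then every 16 weeks for the next two evaluations", then 24 weeks. Scans therefore fall at weeks 8, 16, 24, 40, 56 and 80. One final NE scan moves the date by 8 weeks up to week 24, by 16 weeks up to week 56, and by 24 weeks after that.

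**Direction.** The estimate is S(t) = product of (1 - d/n) over event times up to t. A later censoring date leaves every d unchanged and can only enlarge n at later event times. Each factor therefore rises or stays equal, and so does S(t).

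**Illustration with 15 subjects (invented data).** There are 8 progressions: 3 at week 8, 2 at week 16, 2 at week 24 and 1 at week 40. One subject has no post-baseline scan (censored at first dose). Two are censored on adequate scans at week 24 and two at week 40. Subject A is adequate at week 8 with a final NE at week 16. Subject B is adequate at week 16 with a final NE at week 24.

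| Week | Events | At risk (a) | S (a) | At risk (b) | S (b) |
|---|---|---|---|---|---|
| 8 | 3 | 14 | 78.6% | 14 | 78.6% |
| 16 | 2 | 10 | 62.9% | 11 | 64.3% |
| 24 | 2 | 7 | 44.9% | 8 | 48.2% |
| 40 | 1 | 3 | 29.9% | 3 | 32.1% |

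At week 24:

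- (a) (1 - 3/14)(1 - 2/10)(1 - 2/7) = 0.449
- (b) (1 - 3/14)(1 - 2/11)(1 - 2/8) = 0.482

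Two such subjects raise week-24 PFS by 3.3 points. The median is week 24 under both rules, since both curves first fall below 50% there.

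**Average size at Stage 1.** Cohort sizes come from SAP section 1.2: 20 MCL, 15 DLBCL, 15 FL. The interim is expected about 6 months after last enrolment (SAP section 1.3). Everything else is assumed: exponential PFS with median 13 to 52 weeks, follow-up of 26 to 52 weeks, and 5% dropout per scan, with or without tripling after an NE scan.

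| Assumed NE per scan | Average rise in week-24 PFS, (b) minus (a) |
|---|---|
| 5-10% | about 0.3 to 1.5 points |
| 20% | about 1.6 to 4.1 points |

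With medians of 26 and 52 weeks and 5% NE, the two week-24 estimates were identical in 52-77% of simulated cohorts. The sampling standard deviation of the estimate was 10-14 points.

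**Sensitivity.** A second set at n = 15 and 20 assumed medians of 8 to 32 weeks, 26-week accrual and heavier dropout. With 5-10% NE and 10% dropout per visit, week-24 PFS rose by 0.5 to 1.4 points on average, with 0.3 to 1.5 subjects affected per cohort. With 20% NE and 20% dropout, it rose by 3.1 to 4.2 points, with 1.4 to 3.2 subjects affected. In no replicate was rule (b) lower at week 16, 24 or 40.

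**The case against.** The strongest reply is that this is one missing word. The SAP never says that an NE scan sets the censoring date, and it leaves the term disease assessment undefined; a programmer could read the protocol's qualifier into it. The NE category in SAP section 4.2.2 classifies subjects, not scans, and may include subjects with no post-baseline scan, whom the fallback already covers. The protocol text available does not define adequate, and the protocol's statistical section was not in that text, so the exact contrast cannot be fully checked. The average shift is small beside the sampling error, PFS is descriptive, and the listed censoring reasons give some transparency.

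Most of this stands as a limit on size. It also rules out two stronger readings that a reader might infer. The first is that the SAP makes an NE scan proof of no progression; the text permits that result but does not state it. The second is that the lift should be judged at 100 or 55 subjects with scans beyond a year. Those are full two-stage sizes, reached only if Stage 2 opens, whereas this SAP governs the Stage 1 analysis and becomes the study SAP only if futility is met.

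The reply does not remove the mismatch. The SAP states its own censoring rule, omits a condition that the protocol states, and omits it in all three places. Sampling error is no defence either: it goes both ways, while this shift goes one way and can be avoided.

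**Conclusion.** The point holds as a conflict between SAP and protocol on a major secondary endpoint, and the literal SAP wording can only favour the drug. The wording mismatch and the direction of its effect do not depend on any assumed rate. The size does: it rests on NE rates, dropout and median PFS that the documents do not give, and it is zero if no event-free subject ends on an NE scan. On the assumptions shown, expect a shift in week-24 PFS of up to about 1.5 points at 5-10% NE and up to about 4 points at 20% NE.

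A reader might infer that the go/no-go decision is affected. It is not: the futility guideline in SAP section 1.1 counts CR and PR, and no power figure in section 1.2 involves PFS. The change should be made, but the design does not depend on it.

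**What to change.** In both censoring sentences of SAP section 4.3.1, write *last adequate disease assessment*. Define adequate once, as a post-baseline assessment with an overall response other than NE. Reword the fallback so that subjects with no adequate post-baseline assessment are censored at first dose. This aligns the SAP with the qualifier in protocol section 9.2.2.2 and covers subjects who have only NE scans.

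The cost is SAP wording only, with no new data and no change to sample size or the futility guideline. Some subjects may be censored earlier, so reported PFS may be slightly less favourable.
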